22. GENETIC ANALYSIS

Not applicable.

23. DATA NOT SUMMARIZED OR PRESENTED

The unscheduled visits will not be summarized but listed.

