### **Clinical studies**

A first-in-man, Phase I single ascending dose (SAD) and multiple ascending dose (MAD) study (ANB020-001) in healthy subjects is being performed. The SAD part of the study has been completed and 64 subjects were enrolled in the SAD part. Dosed cohorts in the SAD part included 10, 40, 100, and 300 mg SC and 40, 100, 300, and 750 mg IV (n=32 SC route, n=32 IV route). No significant changes in the vital signs (blood pressure [BP], heart rate [HR], or body temperature), physical examinations, or electrocardiograms (ECG) were noted. A total of 81%

subjects in the placebo group and 79% subjects in the ANB020 group had at least one treatment-emergent adverse event (TEAE) during the study. The most commonly reported TEAEs were upper respiratory infection (50% versus 48% in placebo and ANB020 group, respectively) and headache (31% versus 27% in placebo and ANB020 group, respectively). One serious adverse event (SAE) of decreased neutrophils was reported in the ANB020 750 mg dose group which resolved without sequelae prior to study completion. This event was also considered a serious unexpected adverse reaction and was deemed possibly related to the study treatment. No other observations of decreased neutrophils lower than  $1.5 \times 10^9/L$  were observed. One subject in the ANB020 40 mg dose group, had an increased troponin level which returned to normal prior to study completion. No other significant changes in the laboratory test results were noted.

The PK and pharmacodynamic (PD) data obtained from the Phase I study (ANB020-001, SAD part) have been utilized to determine the route and dose of ANB020 to be used in this study. The PK data generated indicated that a linear PK profile was observed upon ANB020 administration across the dose ranges investigated, regardless of the route, but with less than dose-proportional increases in exposure for the SC dosing. The estimated ANB020 mean terminal  $t_{1/2}$  ranged approximately 14 to 17 days. Persistent and nearly complete inhibition of ex vivo IL-33 stimulated INF- $\gamma$  production in whole blood was observed following a single dose (except 10 mg SC) as soon as 24 hours, and lasting through 84 days (latest time point observed for 300 mg and 750 mg IV).

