6.2. BASELINE

The pre-dose measurement taken prior to ANB020 or placebo administration at randomization [Day 1], i.e. reference start date, will be considered as baseline. For all safety variables, baseline will be last non-missing measurement taken prior to reference start date (including unscheduled assessments or retests).

If the pre-dose measurement and the reference start date coincide, that measurement will be considered baseline.

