6.3. RETESTS, UNSCHEDULED VISITS AND EARLY TERMINATION DATA

Listings will include scheduled, unscheduled, retest and early termination data.

For by-visit summaries, data recorded at the nominal visit will be presented. Unscheduled measurements will not to be included in by-visit summaries but may contribute to the baseline value.

Document: \\ieedc-vnasc01\biosdata\AnaptysBio\ANB020\CYA74392\Biostatistics\Documentation\SAP\Final\20181218

Author:

Version Number: Version Date: 18Dec2018

Reference: CS_WI_BS005

Template No: CS_TP_BS016 Revision 4

Effective Date: 01Apr2016

Clinical Study Report ANB020-004 - Original

AnaptysBio Inc PROTOCOL ANB020-004 Page 19 of 46

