18.3. LABORATORY EVALUATIONS

The following tests will be conducted throughout the study under laboratory evaluations:

Hematology (Hematocrit, Packed Cell Volume [PCV], Hemoglobin, MCH, MCH concentration, MCV, Platelet count, RBC, WBC [absolute], Basophils [absolute and %], Eosinophils [absolute and %], Monocytes [absolute and %], Neutrophils [absolute and %], Lymphocytes [absolute and %], Immunoglobulins [IgA, IgG, IgM, IgE, IgD])

Clinical Chemistry (ALT, Albumin, ALP, AST, Bicarbonate, Bilirubin [Total], Bilirubin [Direct-if total is elevated], Calcium, Chloride, C-reactive Protein (CRP), Creatinine, GGT, Glucose, Potassium, Phosphate [Inorganic], Protein [Total], Sodium, Troponin, Urea, hCG [WOCBP])

Document: \\ieedc-vnasc01\biosdata\AnaptysBio\ANB020\CYA74392\Biostatistics\Documentation\SAP\Final\20181218 Author:

Version Number: 1.0 Version Date: 18Dec2018

Template No: CS_TP_BS016 Revision 4 Reference: CS_WI_BS005

Effective Date: 01Apr2016

AnaptysBio, ANB020 CONFIDENTIAL IND 126765, SN 0035

Clinical Study Report ANB020-004 - Original

AnaptysBio Inc PROTOCOL ANB020-004 Page 31 of 46

STATISTICAL ANALYSIS PLAN

Urinalysis (Bilirubin, Blood, Glucose, Ketones, Leukocytes, Nitrates, pH, Protein, Specific gravity, and Urobilinogen)

The following tests were conducted only at screening:

Virology (Hepatitis B Surface Antigen, Hepatitis C Antibody, HIV Antibodies)

TB (QuantiFERON TB Gold test)

Drugs of Abuse

FSH

Urine Pregnancy-dipstick (prior to IP administration on Day 1)

The actual and change from baseline values at scheduled assessment for each laboratory parameter will be summarized using appropriate descriptive statistics by treatment groups and all available visits.

Frequency count and percentages will be provided for categorical variables.

The following summaries also will be provided for laboratory data:

Incidence of abnormal values according to normal range criteria

Normal, Abnormal NCS and Abnormal CS by test

Shift table for laboratory test parameters from baseline will be summarized at each visit. Percentages will be based on the number of patients in the SAF population with data at baseline and the visit of interest.

Hematology and clinical chemistry data will be reported in System International (SI) units.

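### A post-dose laboratory abnormality seen only on an unscheduled draw is left out of the laboratory abnormality and shift tables, because those tables are by nominal visit and have no worst post-baseline row

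*SAP*

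**What the plan says.** **Baseline.** SAP 6.2 takes the last non-missing value before dosing as baseline for safety variables and expressly admits unscheduled assessments and retests.

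**After baseline.** SAP 6.3 says "For by-visit summaries, data recorded at the nominal visit will be presented" and continues: "Unscheduled measurements will not to be included in by-visit summaries but may contribute to the baseline value". SAP 23 is broader: "The unscheduled visits will not be summarized but listed". SAP 6.4 sets windowing to not applicable, so no rule assigns an extra draw to a nominal visit.

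**Laboratory summaries.** SAP 18.3 plans "Incidence of abnormal values according to normal range criteria", a Normal / Abnormal NCS / Abnormal CS summary, and shifts: "Shift table for laboratory test parameters from baseline will be summarized at each visit". For the shifts, "Percentages will be based on the number of patients in the SAF population with data at baseline and the visit of interest". The shells for Tables 14.3.4.1 to 14.3.4.3 and 14.3.5.5 each carry a visit column. None has a row for any or worst post-baseline value.

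**Protocol.** Section 9.4.2 asks for descriptive statistics at each scheduled assessment. It also says, with no limit to scheduled draws, that clinically significant laboratory changes will be both summarized and listed. Section 7.1.2 treats an abnormality that the Investigator considers clinically significant as a laboratory AE, with some latitude where the value fits a current diagnosis.

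**The concern.** Safety and tolerability are a primary objective. SAP 18 plans no statistical comparison of safety data and there is no data monitoring committee, so the descriptive tables are the laboratory safety analysis. If an abnormality is measured only between scheduled visits, the plan collects it and lists it but does not count it by arm in the laboratory tables. A reader who takes the abnormality or shift tables as the incidence would then see too few patients.

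The protocol's account of Phase I shows the type of event: "One serious adverse event (SAE) of decreased neutrophils was reported in the ANB020 750 mg dose group". It was considered possibly related and resolved before that study ended. A laboratory change that comes and goes is what by-visit tables can miss.

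There is also a consistency problem. A clinically significant value from an unscheduled draw, once recorded as an AE, would appear in the TEAE table while the Abnormal CS row for the same parameter shows nothing.

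**Working it through.** The plan gives no figure to reproduce, so the check is mainly one of text.

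**1. Follow one unscheduled value through the plan.**

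| Output | Does the unscheduled value enter? | Source |
|---|---|---|
| Laboratory baseline | Yes, if before dosing | SAP 6.2, 6.3 |
| Observed and change tables by visit | No | SAP 6.3 |
| Normal / NCS / CS tables 14.3.4.1 to 14.3.4.3 | No: visit rows only | SAP 6.3, 23; shells |
| Shift table 14.3.5.5 | No: visit rows only | SAP 6.3, 18.3, 23; shell |
| Listings | Yes | SAP 6.3 |
| TEAE tables | Only if judged clinically significant and recorded as an AE | Protocol 7.1.2; SAP 18.1 |

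An out-of-range value on an unscheduled draw that is not recorded as an AE therefore reaches no summary. One that is recorded as an AE reaches the AE tables but not the laboratory tables.

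**2. Size per patient.** Protocol 6.2.2 plans 12 patients per arm. One patient is 1/12 = 8.3%, so an arm's row could read 0/12 instead of 1/12.

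**3. Room between scheduled draws.** Protocol 7.2 schedules post-screening hematology on Days 1, 2, 8, 22, 36, 64, 85, 106 and 127. The gaps g are 1, 6, 14, 14, 28, 21, 21 and 21 days.

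As an illustration, suppose an abnormality lasts L whole days, with onset equally likely on each day from Day 2 to Day 127 − L. Both are assumptions, since the documents give neither duration nor onset. Visit windows are ignored.

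- Onset days that touch no scheduled draw = sum over gaps of max(0, g − L).
- Possible onset days = 126 − L.

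| L (days) | Onsets with no scheduled draw | Possible onsets | Share |
|---|---|---|---|
| 5 | 1 + 9 + 9 + 23 + 16 + 16 + 16 = 90 | 121 | 74% |
| 7 | 7 + 7 + 21 + 14 + 14 + 14 = 77 | 119 | 65% |
| 10 | 4 + 4 + 18 + 11 + 11 + 11 = 59 | 116 | 51% |
| 14 | 14 + 7 + 7 + 7 = 35 | 112 | 31% |
| 21 | 7 | 105 | 7% |

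These shares say how often a short abnormality fits between scheduled draws. They do not say how often it would be measured. The exclusion rule matters only if an extra draw is taken in that interval, and the documents give no rate for that.

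**The case against.** The strongest reply is that the important events are already captured. Protocol 7.1.2 has the Investigator review laboratory results at every time point, and a clinically significant abnormality is generally an AE whichever draw finds it. Protocol 7.1.1 names neutropenia among its examples of medically significant events. AEs are tabulated by arm, severity, relationship and seriousness. This stands. A reader might infer that a repeat of the Phase I neutrophil SAE would vanish from the summaries. The documents do not support that: a similar SAE here would be in the AE tables. The Phase I case also occurred at 750 mg, against 300 mg in this trial, and no duration is given for it.

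Other points that stand:

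- **Nothing is lost.** The values are listed. With about 24 patients the listings can be read, and unblinded safety listings are also reviewed after Day 36 and Day 64 (SAP 4.2, 21).
- **Not every repeat is barred.** SAP 6.3 and 23 refer to unscheduled measurements and visits. A retest recorded under a nominal visit is not expressly excluded, although the SAP has no rule for choosing between two values at one visit.
- **Early termination data are not excluded.** SAP Appendix 2 places them in the Day 127 row.
- **The mechanism is limited.** If an abnormal scheduled value prompts the repeat, that scheduled value stays in the tables. If no extra draw is made, no added row can recover the event. That extra draws tend to follow suspicion of an abnormality is plausible but is not stated.
- **By-visit tables follow the protocol**, and a last pre-dose baseline that may be unscheduled is an ordinary definition.

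None of this puts an abnormality seen only on an unscheduled draw into the laboratory tables. Nor does it square those tables with the Protocol 9.4.2 statement on clinically significant changes.

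**Conclusion.** The point holds in a narrow form. For a post-dose abnormality measured only on an unscheduled draw, with non-abnormal scheduled values on either side, the laboratory abnormality and shift tables show nothing. The listings show it, and the TEAE tables show it only after a clinical-significance judgement and AE entry. The per-patient laboratory incidence can therefore be understated, by 8.3 percentage points of a 12-patient arm for each such patient. The Abnormal CS rows can also conflict with the AE tables.

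The documents do not support saying that the incidence will be understated: they give no frequency of unscheduled draws, and the shares in the working rest on assumed durations and uniform onset. No hypothesis test is affected, and the efficacy and pharmacodynamic analyses are untouched. This is a cheap improvement to reporting under a primary safety objective, not a fault that undermines the trial.

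**What to change.** Keep the by-visit tables as planned. In Tables 14.3.4.1, 14.3.4.2, 14.3.4.3 and 14.3.5.5, add one row per parameter for the worst post-baseline value, drawn from scheduled, unscheduled and retest results. For the shift table, define worst separately in the low and high directions. Add a sentence to SAP 6.3 and to SAP 23 exempting this row from the exclusion of unscheduled data.

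No new data are needed. The cost is a little SAP wording, one derived record per patient and parameter (two where both directions apply), and a reported incidence that may be slightly less favourable.

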APPENDIX 1. PARTIAL DATE CONVENTIONS

Imputed dates will NOT be presented in the listings.

Algorithm for Treatment Emergence of Adverse Events:

START DATE	STOP DATE	ACTION
Known	Known	If start date < study med start date, then not TEAE
		If start date ≥ study med start date, then TEAE
	Partial	If start date < study med start date, then not TEAE
		If start date ≥ study med start date, then TEAE

Document: \\ieedc-vnasc01\biosdata\AnaptysBio\ANB020\CYA74392\Biostatistics\Documentation\SAP\Final\20181218

Author: Version Number: Version Date: 18Dec2018

Template No: CS_TP_BS016 Revision 4 Reference: CS_WI_BS005

Effective Date: 01Apr2016

29 June 2020 40 STATISTICAL ANALYSIS PLAN

IMS Health & Quintiles are now

AnaptysBio Inc PROTOCOL ANB020-004 Page 40 of 46

START DATE	STOP DATE	ACTION
	Missing	If start date < study med start date, then not TEAE
		If start date ≥ study med start date, then TEAE
Partial, but known	Known	Not TEAE
components show that it cannot be on	Partial	Not TEAE
or after study med	Missing	Not TEAE
start date		
Partial, could be on	Known	If stop date ≥ study med start date, then TEAE
or after study med start date	Partial	Impute stop date as latest possible date (i.e. last day of month if day unknown or 31st December if day and month are unknown), then:
		If stop date < study med start date, then not TEAE
		If stop date ≥ study med start date, then TEAE
	Missing	Assumed TEAE
Missing	Known	If stop date < study med start date, then not TEAE
		If stop date ≥ study med start date, then TEAE
	Partial	Impute stop date as latest possible date (i.e. last day of month if day unknown or 31st December if day and month are unknown), then: If stop date < study med start date, then not TEAE
		If stop date ≥ study med start date, then TEAE
	Missing	Assumed TEAE

Document: \\ieedc-vnasc01\\biosdata\AnaptysBio\ANB020\CYA74392\\Biostatistics\Documentation\SAP\Final\20181218 Author: \text{Version Number: } 1.0

Version Number: 1.0 Version Date: 18Dec2018

Reference: CS_WI_BS005

Template No: CS_TP_BS016 Revision 4

Effective Date: 01Apr2016

AnaptysBio Inc PROTOCOL ANB020-004 Page 41 of 46

Algorithm for Prior / Concomitant Medications:

START DATE	STOP DATE	ACTION
Known	Known	If stop date < study med start date, assign as prior
		If stop date >= study med start date assign as concomitant
	Partial	Impute stop date as latest possible date (i.e. last day of month if day unknown or 31st December if day and month are unknown), then:
		If stop date < study med start date, assign as prior If stop date ≥ study med start date, assign as concomitant
	Missing	If stop date is missing, it could never be assumed a prior medication, assign as concomitant
Partial	Known	Impute start date as earliest possible date (i.e. first day of month if day unknown or 1st January if day and month are unknown), then:
		If stop date < study med start date, assign as prior If stop date ≥ study med start date, assign as concomitant

Document: \\ieedc-vnasc01\biosdata\AnaptysBio\ANB020\CYA74392\Biostatistics\Documentation\SAP\Final\20181218

[figure not shown]
Author: Version Number: 1.0 Version Date: 18Dec2018

Template No: CS_TP_BS016 Revision 4 Reference: CS_WI_BS005

Effective Date: 01Apr2016

29 June 2020 42

Clinical Study Report ANB020-004 - Original

START DATE	STOP DATE	ACTION
	Partial	Impute start date as earliest possible date (i.e. first day of month if day unknown or 1st January if day and month are unknown) and impute stop date as latest possible date (i.e. last day of month if day unknown or 31st December if day and month are unknown), then:
		If stop date < study med start date, assign as prior If stop date >= study med start date, assign as concomitant
	Missing	If stop date is missing, it could never be assumed a prior medication, assign as concomitant
Missing	Known	If stop date < study med start date, assign as prior If stop date >= study med start date, assign as concomitant
	Partial	Impute stop date as latest possible date (i.e. last day of month if day unknown or 31st December if day and month are unknown), then:
		If stop date < study med start date, assign as prior
		If stop date >= study med start date, assign as concomitant
	Missing	Assumed concomitant

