6.1. REFERENCE START DATE AND STUDY DAY

The reference start date is defined as the day of the dose administration of study treatment (Day 1), and will appear in every listing where an assessment date or event date appears.

The study day will be calculated from the study treatment start date and will be used to show start/stop day of assessments and events.

If the date of the event is on or after the reference date then:

Study Day = (date of event – reference date) + 1

If the date of the event is prior to the reference date then:

Study Day = (date of event – reference date)

If the event date is partial or missing, Study Day, and any corresponding durations will appear missing for that partial date in the listings.

Refer to Appendix 1 for more details.

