18.1. ADVERSE EVENTS

AEs will be coded using MedDRA version 19.1.

Treatment emergent adverse events (TEAEs) are defined as AEs that started or worsened in severity on or after the date and time of the study drug infusion.

Non-treatment emergent adverse event (Non-TEAE) will be defined as any AE that started on or after the date of informed consent and before the administration of study drug.

AEs with missing start dates will be considered treatment-emergent. AEs with missing stop dates or

Document: \\ieedc-vnasc01\biosdata\AnaptysBio\ANB020\CYA74392\Biostatistics\Documentation\SAP\Final\20181218 \\
Author: \quad \text{Version Number:} \quad 1.0

Version Date: 18Dec2018

Template No: CS_TP_BS016 Revision 4 Reference: CS_WI_BS005

Effective Date: 01Apr2016

AnaptysBio, ANB020 CONFIDENTIAL

IND 126765, SN 0035

Clinical Study Report ANB020-004 - Original

AnaptysBio Inc PROTOCOL ANB020-004 Page 29 of 46

IQVIA STATISTICAL ANALYSIS PLAN

with stop dates after the end of the study date will be considered to have been ongoing at the end of the study.

The severity of AEs will be characterized as "mild, moderate, severe" according to the following definitions:

Mild events are usually transient and do not interfere with the patient's daily activities

Moderate events introduce a low level of inconvenience or concern to the patient and may interfere with daily activities

Severe events interrupt the patient's usual daily activity

Missing severity will be assumed to be the worst severity case i.e. 'severe'; however, in the listing, it will be displayed as missing.

The causal relationship between the study drug and the AE will be characterized as "Unrelated, Unlikely, Possible, Probable, and Unknown (unable to judge)".

The summaries will be presented as "Related" versus "Not Related".

Categories "Unrelated" and "Unlikely" will be mapped to "Not Related", while the categories "Possible", "Probable" and "Unknown" will be mapped to "Related".

Missing relationship will be assumed to be the worst severity case i.e. 'Related; however, in the listing, it will be displayed as missing.

An overview of adverse event along with the number and percentage of patients experiencing TEAEs, for each treatment group will be provided.

If patient has multiple TEAEs by severity and/or multiple relationship with study drug, worst case severity and the worst-case relationship to the study drug will used for overview tabulation.

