- If Date of assessment ≥ Reference Start Date then Study Day= (Date of assessment Reference start date) +1, else Study Day= Date of assessment Reference start date.

Programming Note (not part of table): Sort by treatment, patient number and visit.

Document: Author: Version Number: Version Date: 1.0 18Dec2018

127

AnaptysBio Inc. PROTOCOL ANB020-004 Page 28 of 41

Listing 16.2.6.6 Time to first asthma exacerbation - Full Analysis Set

Patient No./ Treatment	Date of Randomization	Date of first Exacerbation	Time of first Exacerbation	Censored
XXX/ XXX/	DDMMMYYYY	DDMMMYYYY	xxxx	Yes
XXX/ XXX/	DDMMMYYYY	DDMMMYYYY	xxxx	No

Programming Note (not part of table): Sort by treatment, patient number and visit.

AnaptysBio Inc. PROTOCOL ANB020-004 Page 29 of 41

Listing 16.2.6.7 Rescue Medication - Safety Analysis Set

Patient No./ Treatment	Age/ Gender	Medication Name	Start Date/ Study Day	End Date/ Study Day/ Ongoing	Dose (Unit)	Frequency	Route	Indication
XXX/ XXX/	32/ Male	xxxxx	DDMMMYYYY/ xx	DDMMMYYYY/ xx	xx (xx)	xxxxx	xxxxx	xxxxx
		xxxxx	DDMMMYYYY/ xx	Ongoing	xx (xx)	xxxxx	xxxxx	xxxxx
XXX/ XXX/	31/ Female	xxxxx	DDMMMYYYY/ xx	DDMMMYYYY/ xx	xx (xx)	xxxxx	xxxxx	xxxxx

Note:

- If Date of assessment ≥ Reference Start Date then Study Day= (Date of assessment – Reference start date) +1, else Study Day= Date of assessment – Reference start date.

Programming Note (not part of table): Sort by treatment, patient number, and start date.

AnaptysBio Inc. PROTOCOL ANB020-004 Page 30 of 41

Listing 16.2.7.1 Adverse Event - Safety Analysis Set

Patient No./ Treatment	Age/ Gender	System Organ Class/ Preferred Term/Verbatim Term	Start Date/ Study Day	End Date/ Study Day	Did AE Occur Prior to the Start of IP?	Severi ty	TEAE	Final Outcome	Action taken with the Study Drug	Relationship to Study Drug	Serious/ Criteria ^[a]	Did the AE Cause the Patient to Discontinue from the Study?	Was Patient Treated for AE?
XXX/ XXX/	32/ Male	xx/xx/xx	DDMMMY YYY/ xx	DDMMMY YYY/ xx	No	Severe	Yes	Recovered	Dose interrupted	Unlikely	Yes/ XXX	Yes	No
XXX/ XXX/	31/ Female	xx/xx/xx	DDMMMY YYY/ xx	DDMMMY YYY/ xx	Yes	Mild	No	Fatal	Drug permanently discontinued	Possible	Yes/ XXX	Yes	Yes

Note:

- [a]: If SAE led to death, then date of death and primary/ secondary cause of death are provided; if required hospitalization, then date of admission and date of discharge are provided.

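### The SAP's two rules for treatment emergence disagree on Day 1 pre-dose events, on earlier events that worsen after dosing, and on missing start dates, and nothing says which rule governs

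*SAP*

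**What the plan says.** **SAP 18.1.** Treatment-emergent adverse events (TEAEs) are "AEs that started or worsened in severity on or after the date and time of the study drug infusion". The footnote to table shell 14.3.1.1 and the note to listing shell 16.2.7.1 repeat this definition. A non-TEAE is "any AE that started on or after the date of informed consent and before the administration of study drug". On absent onset dates, 18.1 states: "AEs with missing start dates will be considered treatment-emergent".

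**SAP Appendix 1.** Under the title "Algorithm for Treatment Emergence of Adverse Events" it gives a grid of start-date and stop-date situations. When the start date is known the rule is "If start date < study med start date, then not TEAE", and otherwise "If start date ≥ study med start date, then TEAE". When the start date is missing, a stop date before study medication makes the event not treatment-emergent.

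**SAP 6.1.** The reference start date is a calendar day, the day of dosing.

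**Listing shell 16.2.7.1.** It carries a column "Did AE Occur Prior to the Start of IP". Appendix 1 does not use it.

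**The concern.** Safety and tolerability is one of the two primary objectives, and SAP 18.1 builds nearly all of its adverse event tables on TEAEs. A definition by date and time of onset or worsening cannot be reproduced by an algorithm that looks only at the date of onset. The title of the appendix refers to partial dates, but its first row covers events with both dates fully known, so the conflict is not confined to incomplete data.

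The two directions of error differ in kind. A Day 1 event before the infusion cannot be caused by study drug, so counting it adds background events to both arms. An event that worsens after the infusion can reflect a drug effect. Dropping it from the TEAE tables is therefore not conservative.

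**Working it through.** The plan gives no figure to reproduce. The check applies both rules to the same events.

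**Can the disputed events occur?**
- Protocol 6.2.6 puts the ACQ, blood samples, FeNO and pre- and post-bronchodilator spirometry before the infusion on Day 1, so there is a pre-dose period on the dosing date.
- Protocol 7.1.1.1 requires adverse events to be recorded from informed consent, and the screening visit is 7 to 14 days before Day 1. Events with onset before the dosing date will therefore be in the database.

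**Rules as coded, for known start dates**
- 18.1: TEAE if the onset date-time, or the date-time of worsening, is at or after the infusion.
- Appendix 1: TEAE if the onset date is on or after the dosing date.

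| Event | 18.1 | Appendix 1 | Agree? |
|---|---|---|---|
| Onset in screening, no worsening | not TEAE | not TEAE | yes |
| Onset in screening, worsens on Day 3 | TEAE | not TEAE | **no** |
| Onset Day 1 before infusion, no worsening | not TEAE | TEAE | **no** |
| Onset Day 1 before infusion, worsens on Day 3 | TEAE | TEAE | yes |
| Onset Day 1 after infusion | TEAE | TEAE | yes |
| Onset Day 5 | TEAE | TEAE | yes |

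The rules agree on 4 of 6 patterns and differ on 2. The loss of worsening events is limited to onset on a date before dosing. An event that begins before the infusion on Day 1 and then worsens is a TEAE under both rules, although Appendix 1 reaches that answer through the date of onset.

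**Missing start date, stop date before the dosing date.** 18.1 gives TEAE and Appendix 1 gives not TEAE. With a stop date on or after dosing, or no stop date, both give TEAE.

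**Overlap inside 18.1.** An event that begins before dosing and worsens afterwards meets both the TEAE and the non-TEAE definition, because the latter looks only at onset.

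**Size.** Protocol 6.2.2 plans 12 patients per arm, and percentages use the safety set. One reclassified patient moves a row of an arm by 1/12 = 0.083, or 8.3 percentage points. If a replaced patient had been dosed and the arm reached 13, the shift would be 1/13 = 7.7 points.

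**The case against.** The strongest reply is that Appendix 1 may never override 18.1. Section 18.1 does not refer to it. SAP 6.1, 7.3 and 14 point there for partial or missing dates, while the shells that programmers work from repeat the 18.1 definition. The dummy rows of Listing 16.2.7.1 pair a pre-IP answer of Yes with TEAE No, and of No with TEAE Yes, which fits 18.1. This stands to a degree: a reader might infer that programmers will follow Appendix 1 and that the safety tables will be wrong, and the documents do not support that. They show two conflicting texts without an order of precedence. Dummy rows are not a rule.

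Second, Protocol 7.1.1.1 asks for each event to be recorded separately. If a worsening becomes a new record with its own onset date, Appendix 1 already makes it a TEAE. That would remove the under-count, but the instruction does not mention worsening, and the eCRF is not among the documents.

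Third, the practical effect is limited. SAP 18 plans no statistical comparison of safety data between arms, non-TEAEs have their own table (14.3.1.9), Listing 16.2.7.1 is not restricted to TEAEs, and the same rule applies to both arms. All of this is true. It lowers the importance of the point but does not tell two programmers how to produce the same table.

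Fourth, a reader might take 8.3 points as the shift in the overall TEAE rate. It is not. In the single-dose part of the Phase I study, 81% of placebo and 79% of ANB020 subjects had at least one TEAE (Protocol 2.1). If rates here were similar, which is an assumption, most patients would keep their any-TEAE status after one event was reclassified.

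**Conclusion.** The inconsistency is real. Appendix 1 contradicts the 18.1 definition for complete dates in two situations, one over-counting and one under-counting, and the missing-start-date rules conflict as well. If Appendix 1 is followed, the classification is wrong by the SAP's own definition. The documents do not establish that it will be followed.

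The number of affected events cannot be derived from the documents. The 8.3 points is a maximum per patient for an affected row at 12 patients per arm; it reaches the any-TEAE row only when the patient has no other TEAE. The under-count rests on the assumption that a worsening is not entered as a new record.

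One further inference should be avoided: that all the data needed to apply 18.1 are already collected. The pre-IP item is seen only in a listing shell, not in the eCRF. Protocol 7.1.1.1 asks for dates of onset, and the listing shows no onset time and no date of severity change. This is a minor point to reconcile, though it touches a primary safety variable.

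**What to change.** Make Appendix 1 follow 18.1.

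1. **Onset on the dosing date:** classify by the item "Did AE Occur Prior to the Start of IP" in Listing 16.2.7.1, or by onset time if it is collected.
2. **Worsening:** add a branch under which an event with onset before dosing whose severity increased on or after dosing is a TEAE. Identify it from a severity-change record or from a new adverse event record, whichever the eCRF holds. In 18.1, restrict the non-TEAE definition to events that did not worsen after dosing.
3. **Missing start date:** state one rule in both places. The Appendix 1 stop-date rule is a reasonable choice, since an event that ended before dosing cannot be treatment-emergent. Aligning in the other direction would also remove the conflict.

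While the grid is open, fill the row for a partial start date that could fall on or after dosing with a known stop date: it gives no outcome when the stop date precedes dosing.

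The cost is a few lines of SAP text. SAP Section 1 provides for an amendment if the change comes after database lock or unblinding. Items 1 and 2 need one check of the eCRF first, to confirm that the pre-IP item exists and how worsening is recorded. If worsening is not recorded at all, the SAP should say that this part of the definition cannot be applied.
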